Preliminary human data indicate curcumin supplementation improves surrogate markers of liver disease and of metabolic risk in NAFLD patients^{20, 21}. The combination of curcumin with phospholipids greatly improves oral bioavailability of curcumin, allowing greater systemic concentrations and delivery to target organs^{22, 23}, and curcumin-phosphatidylcholine phytosome complex administration for up to 18 months was well-tolerated, safe²⁴ and improved clinical end-points and inflammatory parameters in patients with osteoarthritis, uveitis and chronic kidney disease (CKD)^{25, 26, 27}.

2. Research Hypothesis and Aims

On the basis of above-mentioned data, we hypothesized that treatment with phytosomal curcumin would result in significant improvement in liver histology in patients with NASH.

Key secondary hypotheses include tolerability and safety of phytosomal curcumin and the potential to improve NASH-related CKD, systemic inflammation, glucose and lipid metabolism.

To test this hypothesis, we designed a phase II, multicentre, double-blinded, placebo-controlled randomized controlled trial (RCT).

3. Study Design setting and timeline

This is a 72-week, investigator-initiated, multicentre, randomized, double-blinded, placebo-controlled trial of treatment with phytosomal curcumin 1 g daily for adults with biopsy-proven NASH. Screening was undertaken within 14 days of randomisation to assess eligibility and collect baseline data. Patients who satisfied the eligibility criteria were randomly assigned (1:1) to receive oral phytosomal curcumin 1 g daily (experimental) or placebo (control). After which, a 12-week washout period is scheduled.

The trial will be conducted at two University hospitals (HUMANITAS Gradenigo, Turin, Italy, and Città della Salute e della Scienza, Turin, Italy) between May 25th, 2018 and Dec 30th, 2022.

The primary outcome measure will be assessed using an intention-to-treat analysis of the proportion of evaluable patients achieving an improvement in liver histology between liver biopsies at baseline (within 6 months of screening) and after 72 weeks of treatment. Histological improvement will be defined as a

combination of resolution of active steatohepatitis and no worsening in fibrosis (assessed by Kleiner Fibrosis score²⁸; detailed in outcome section).

4. Ethics and regulatory approval

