Histological NASH resolution (defined by the NASH Clinical Research Network as no more than mild residual inflammatory cells [score of 0 or 1] and no hepatocyte ballooning [score of 0]) **and** no worsening of liver fibrosis (with worsening defined as an increase of one stage or more on the Kleiner fibrosis classification scale) after 72 weeks, in line with regulatory perspectives^{31,32}.

Secondary outcome measures

Liver-centered histological outcomes:

1) a ≥ 1 stage improvement in fibrosis and no worsening of NASH (with worsening defined as an increase of ≥ 1 point in either the lobular inflammation score or the hepatocyte ballooning score according to the NASH Clinical Research Network criteria) after 72 weeks

2) improvement in clinically significant fibrosis³³, defined by the proportion of patients with baseline fibrosis stage ≥ 2 who have fibrosis stage 0-1 at EOT, without worsening of NASH.

3) improvement in advanced fibrosis, defined by the proportion of patients with baseline fibrosis stage 3-4 who have fibrosis stage 0-2 at EOT, without worsening of NASH.

3) a ≥ 2 -point improvement in NAFLD activity score (NAS), with at least 1 point improvement in either ballooning or lobular inflammation score;

4) individual components of the NAFLD activity score (steatosis, hepatocyte ballooning, lobular inflammation) and the Kleiner fibrosis stage. Fibrosis stages 1a, 1b, and 1c were considered stage 1 for the purposes of analysis.

Liver-centered non-histological outcomes:

4) changes from baseline to 72 weeks in serum liver enzyme concentrations, improvement in noninvasive markers of liver disease severity, including computerized sonographic hepato-renal ratio (which correlates closely with histologic and ¹H magnetic resonance spectroscopy steatosis^{34,35, 36,37,38}, see **Analytical**

Methods subheading), serum cytokeratin-18 fragments(a marker of NASH), NAFLD fibrosis score, FIB-4 and serum lumican (as markers of fibrosis)(see supplementary material).

The extracellular matrix proteoglycan lumican was chosen because its circulating levels have been shown to be a reliable marker not only of hepatic fibrosis but also of active hepatic fibrosis deposition, its expression is upregulated by Nf-kB, and its levels have been shown to differentiate histologically progressive, fibrosing NASH from mild, nonprogressive NAFLD^{39, 40, 41}

Non liver-centered outcomes

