9.1 Power analysis

Sample size justification. There are no data on liver histological response to curcumin.

The sample size was calculated using A'Hern's single stage phase II methodology⁷⁷ with a significance level of 0.05 (type I error) and power of 0.90 (type II error).

Based on previous trials showing an improvement in surrogate markers of NAFLD with curcumin ranging 20- 50% of patients, depending on different liver disease surrogates, curcumin dose, formulations and treatment duration vs. 15% with lifestyle intervention⁷⁸, the design required 21 evaluable patients in the phytosomal curcumin group; after allowing for a 10% dropout rate, at least 25 subjects per arm were needed to detect a significant difference in the primary outcome. The study A'Hern's design stipulates that at least eight (38%) out of 21 patients in the phytosomal curcumin group have to achieve histological improvement for phytosomal curcumin to be deemed worthy of further investigation with a phase III trial⁸⁴

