9.2 Methods for analysis of primary and secondary outcomes

All evaluable patients will be analysed on an intention-to-treat basis. Evaluable patients are defined as those who have had an end-of-treatment biopsy, irrespective of the amount of treatment they have received.

Patients will be categorised as either achieving the primary histological endpoint (ie, NASH resolution) or not. The proportion of patients with a reported improvement in liver histology will be presented and compared across treatments descriptively with 95% CIs.

The primary analysis will be based on a Cochran–Mantel–Haenszel test based on all randomised patients for the in-trial period with missing data handled as non-responders. The common risk ratio between phytosomal curcumin and placebo was estimated along with exact 95% CI. To test for superiority, the exact two-sided p-value was calculated as the sum of probabilities of outcomes having equal or lower probability than the observed outcome under the null hypothesis.

Adjustments for multiplicity testing in the primary analysis will be performed with the use of the Benjamini-Hochberg procedure; each active-treatment group was compared with the placebo group. Two-sided P values <0.05 were considered statistically significant.

An unpowered, preplanned secondary analysis of categorical outcome measures will be done using the χ^2 test or Fisher exact test, as appropriate, of the difference between the proportions of patients with histological improvement in each treatment group.

A preplanned logistic regression analysis will be undertaken to determine the treatment effect when adjusted for the stratification variables (diabetes status, obesity status, fibrosis stage, CKD status) and trial site. We will calculate adjusted relative risks using the Mantel-Haenszel test. Two-sided P values <0.05 will be considered statistically significant in all analyses.

Continuous secondary outcome measures will be compared between treatment groups using linear

regression, adjusting for parameter baseline values and allocated treatment (as model covariates, equivalent to ANCOVA), with multilevel modelling for key continuous outcome measures to account for repeated measures within each patient.

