9.5 Prespecified additional subgroup and sensitivity analyses

As previously specified, the primary imputation method for missing data will be the non-responder imputation for primary and secondary dichotomous outcomes.

To investigate the sensitivity of the results of the primary analysis with regard to the handling of missing data, a sensitivity analysis using imputation based on unconditional reference was performed for the primary and secondary outcomes. The analysis is based on the same type of non-parametric method as for the primary analysis but with missing data handled by a method of multiple imputation which assumes that the unobserved outcomes are well described by the observed outcomes of the subjects in the placebo arm with similar baseline characteristics. The imputation is done by random sampling of observed outcomes from placebo subjects with the same baseline diabetes status, obesity status, fibrosis stage and CKD status. Multiple (100) replicates of a complete data set will be generated and, for each complete data set, the log risk ratios will be estimated together with the asymptotic standard errors. The estimates and standard errors for the 100 complete data sets were pooled using Rubin's rule to obtain a single estimate of the risk ratio and a 95% confidence interval. The analysis differs from the primary analysis in that it assumes that subjects with missing week 72 data had the same chances of NASH resolution as subjects with week 72 data in the placebo group. If there will be more missing week 72 data in the phytosomal curcumin group than in the placebo group, this analysis would be less conservative than the primary analysis and probably give a better estimate of the treatment effect. The handling of missing data is analogous to the "copy reference" approach for longitudinal normal data presented by Carpenter et al.⁸¹

We also plan to perform the following subgroup analyses to assess the effect of the following characteristics on main efficacy and safety outcomes:

-trial site

-diabetes status, obesity status, CKD status, fibrosis stage (F3-4 vs F0-2)

-per protocol analysis (only patients who completed treatment, had EOT liver biopsy and no major protocol deviations will be included).

All analyses will be carried out with Easy R ver1.61, Saitama, Japan⁸².

10. Ethics and Dissemination

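### Section 9.2 assigns primary responder status on NASH resolution alone and omits the no-worsening-of-fibrosis condition that sections 3 and 7 make part of the primary outcome

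*Protocol*

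**What the plan says.** The protocol describes the primary endpoint in four places.

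- **Section 3 (Study Design).** Histological improvement, the basis of the primary outcome, is a "combination of resolution of active steatohepatitis and no worsening in fibrosis".
- **Section 7 (Primary outcome measure).** There are two conditions joined by a bold *and*. The first is NASH resolution, with its own definition: "no more than mild residual inflammatory cells [score of 0 or 1] and no hepatocyte ballooning [score of 0" for the ballooning component. The second is "no worsening of liver fibrosis (with worsening defined as an increase of one stage or more on the Kleiner fibrosis classification scale".
- **Section 9.2.** The classification rule is "Patients will be categorised as either achieving the primary histological endpoint (ie, NASH resolution) or not". The next sentence changes the term: "The proportion of patients with a reported improvement in liver histology will be presented and compared across treatments descriptively with 95% CIs".
- **Section 9.5.** In explaining the reference-based imputation for the primary and secondary outcomes, the text says it assumes that patients without week 72 data "had the same chances of NASH resolution as subjects with week 72 data in the placebo group".

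No sentence says that NASH resolution is used as a short name for the two-part outcome.

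**The concern.** The parenthesis in 9.2 begins with *ie*, so it equates the primary endpoint with NASH resolution. Section 7 gives that term a definition of its own in which fibrosis plays no part. An analyst who codes the responder variable from section 9, using the protocol's own definition of the term, would code only the first of the two conditions.

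The variable at stake is the primary one. Literal 9.2 can only add responders, but it can add them in either arm, so the comparison could move in either direction. It would also count as successes patients whose fibrosis had progressed, which the outcome in section 7 is built to prevent. This is not detail that can be left to a statistical analysis plan: the protocol states the rule in two ways, and a plan that followed one would depart from the other.

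**Working it through.** **1. The two rules side by side.** Each patient is classified by whether NASH resolves (inflammation 0–1 and ballooning 0) and whether fibrosis rises by at least one Kleiner stage.

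| NASH resolved | Fibrosis worsened | Section 7 | Literal 9.2 |
|---|---|---|---|
| yes | no | responder | responder |
| yes | yes | **non-responder** | **responder** |
| no | no | non-responder | non-responder |
| no | yes | non-responder | non-responder |

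The rules differ in one cell only.

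**2. The plan's own figure.** Section 9.1 requires at least 8 responders among 21 evaluable curcumin patients, "with a significance level of 0.05 (type I error) and power of 0.90 (type II error"). It does not name the null and target rates. Assuming p0 = 0.20 and p1 = 0.50 (the ends of the 20–50% range quoted there), the smallest exact single-stage design is n = 21, r = 8:

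- P(X ≥ 8 | 21, 0.20) = 0.043
- P(X ≥ 8 | 21, 0.50) = 0.905

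This reproduces the stated design. The calculation does not use the disputed wording, and 9.1 states its rule in terms of histological improvement, which section 3 defines as the composite.

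**3. Sensitivity to one patient.** Section 5.1 plans 52 patients and section 5.5 allocates 1:1, so 52/2 = 26 per arm. Two-sided Fisher exact p-values:

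| Curcumin | Placebo | p |
|---|---|---|
| 11/26 | 3/26 | 0.027 |
| 10/26 | 3/26 | 0.052 |
| 12/26 | 4/26 | 0.034 |
| 11/26 | 4/26 | 0.064 |

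In each pair, moving one curcumin patient across the cell where the rules differ moves the result across 0.05. The planned primary test is an exact Cochran–Mantel–Haenszel test; Fisher's test stands in for it here.

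**4. How often the verdict might differ.** Let f be the share of NASH resolvers who gain at least one stage, equal in both arms. The documents give no value for f, so this is an assumption shown over a range. The entries are the probability that the Fisher verdict at 0.05 differs between the two definitions, at 26 per arm:

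| f | resolution 50% vs 20% | resolution 38% vs 15% |
|---|---|---|
| 1% | 2% | 2% |
| 2% | 4% | 3% |
| 5% | 8% | 6% |
| 20% | 22% | 17% |

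**5. Power, if the target rate meant resolution alone.** The composite rate would then be 0.50 × (1 − f). The power of the 8-of-21 rule is 0.905 at f = 0, 0.861 at 5%, 0.803 at 10% and 0.650 at 20%. This is conditional: section 9.1 draws its rates from surrogate markers and does not say which histological definition they stand for.

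**The case against.** The strongest reply is that 9.2 does not define an endpoint. It refers to the primary histological endpoint, which has one full definition, in section 7, matched by section 3. The surrounding text favours shorthand. The next sentence of 9.2 and the decision rule in 9.1 both speak of histological improvement. The exploratory NF-kB analysis in 9.2 names NASH resolution and fibrosis improvement as the histological responses, although section 7 attaches a second condition to each, so the authors seem to shorten both composites in the same way. I accept this as the probable intention. It does not remove the defect: the short label is itself a defined term with a narrower meaning, and it appears in the sentence that fixes responder status.

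Three stronger readings are tempting and are not supported.

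- A reader might infer that the protocol sets up two rival primary endpoints. It does not; one definition is given in full and the other is a parenthesis that omits half of it.
- A reader might infer that 9.5 imputes NASH resolution alone. Its operative text samples the observed outcomes of placebo patients for the primary and secondary outcomes. The phrase "subjects with missing week 72 data had the same chances of NASH resolution" occurs only in a later sentence that explains the assumption.
- A reader might infer that the fibrosis safeguard is lost. Section 7 still stands, fibrosis is staged on every biopsy (section 8.1.1), and fibrosis stage is a secondary outcome.

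It is also fair to say that any trial of this size is fragile to one patient. The p-values in the working show what a reclassification could do, not that one will occur.

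**Conclusion.** Wrong as written. The classification sentence in 9.2 omits a condition that sections 3 and 7 make part of the primary outcome. The conflict is confined to patients who resolve NASH and also gain at least one Kleiner stage.

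That the two texts differ rests on the protocol alone and needs no assumption. The size of the effect is not established. One reclassified patient can move the verdict at about 26 per arm, but the frequency figures, from about 2% at f = 1% to 22% at f = 20%, depend on an assumed f, on assumed response rates, on Fisher's test in place of the planned one, and on 9.2 being applied literally. They are illustrations. The intended endpoint can be inferred, so this is a correction to make and not a flaw in the design. The primary responder rule should still not depend on inference.

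**What to change.** In section 9.2, replace the parenthesis after the primary histological endpoint with: *(NASH resolution and no worsening of fibrosis, as defined in section 7)*. In section 9.5, change the explanatory sentence so that the assumed chance refers to the same composite. If resolution irrespective of fibrosis is also of interest, list it separately as an exploratory outcome.

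The cost is two wording changes. The sample size, the 8-of-21 rule, the test and the trial procedures stay as they are. The one downside is that the response rate under the composite may be slightly lower than under resolution alone.

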5.1 Eligibility criteria

Eligible adult patients (≥ 18 years old) were identified and recruited at the participating trial site centres starting in August 2018 and ending by June 2022, 52 patients will be recruited. Participating trial centres will include the Liver and Metabolic Units at the Humanitas Gradenigo Hospital (Turin) since August 2018), and the Metabolic Unit of Dept of Medical Sciences at the Città della Salute e della Scienza hospital (Turin) since Sept 2018).

All trial participants will give informed written consent at the beginning of the screening visit prior to undergoing any tests and procedures needed to assess eligibility.

Eligibility for the trial will be determined at screening visit 1 by standard blood tests, clinical history (including written-confirmation of drug history where necessary) and physical examination to identify other illnesses or contraindications for participation.

Patients who satisfied the eligibility criteria trial at both sites will be offered to take part in a metabolic mechanistic substudy. The substudy involves a standard Oral Glucose tolerance Test (OGTT) and a standard Oral Fat Tolerance Test (OFTT) on three admissions (at least 24 hours apart from each other) and an indirect calorimetry test at the two participating centres on visits 2 (pretreatment) and 8 (4 weeks

post-treatment). A detailed summary of the metabolic substudy will be published separately. A patient's decision to partake or withdraw from the metabolic substudy will not affect their participation in the main 72-week trial.

A schematic view of trial schedule and design is presented in **Figure 1**.

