5.5 Randomization, stratification and blinding

Randomization and stratification

Participants meeting all the eligibility criteria and providing written informed consent will be randomized centrally on a 1:1 basis to either of the two-study treatments (phytosomal curcumin vs placebo) using computer generated randomization. To ensure even distribution between groups in key baseline covariates, randomization will be stratified into blocks of 4 according to the following variables: diabetes status (present vs. absent), obesity status (present vs. absent), fibrosis stage (stage F3-4 vs. stage 0-2), CKD (present vs. absent). Trial participants will be allocated a unique trial identification number to preserve patient confidentiality and enable the study to be double-blinded. Patients, investigators, assessors, trial site staff, and the sponsor (except for specific laboratory staff and individuals responsible for safety) remained blinded to treatment assignment throughout the trial.

Medication preparation and blinding/unblinding procedures

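### The preplanned adjusted logistic model puts six slopes on about 14-16 expected responders, so an ordinary maximum-likelihood fit would overstate a real effect's odds ratio by roughly 25-50%

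*Protocol*

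**What the plan says.** Protocol section 9.2 states: "A preplanned logistic regression analysis will be undertaken to determine the treatment effect when adjusted for the stratification variables", lists diabetes, obesity, fibrosis stage and CKD, and adds trial site. The sentence after it promises adjusted relative risks by Mantel-Haenszel. Two-sided 0.05 is the criterion for all analyses. No fitting method, test or odds ratio is named for the logistic model.

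The other facts that fix the model's size are these:

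- Section 5.5 makes each stratifier two-level: "diabetes status (present vs. absent), obesity status (present vs. absent), fibrosis stage (stage F3-4 vs. stage 0-2), CKD (present vs. absent". Patients are "randomized centrally on a 1:1 basis" in blocks of 4.
- Section 3: "The trial will be conducted at two University hospitals", so site takes one term.
- Section 5.1: "52 patients will be recruited". Section 9.1 says "at least 25 subjects per arm were needed to detect a significant difference in the primary outcome".
- Section 9.1 gives the comparator as "vs. 15% with lifestyle intervention". It quotes 20-50% for curcumin on surrogate markers, says that histological response data are lacking, and sets a go rule of 8 of 21 (38%).
- Sections 9.2 and 9.3 count missing outcomes as non-response, which cannot add responders.

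The primary analysis in 9.2 is a Cochran-Mantel-Haenszel test with exact inference, not this model.

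**The concern.** Maximum-likelihood logistic regression pushes a non-zero log odds ratio away from zero when responders are few for the number of coefficients. If a covariate level happens to contain no responders, or only responders, its coefficient has no finite estimate. Here the protocol itself fixes the covariate list and the sample size, so the mismatch does not come from a detail left to a later plan.

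What is at stake is the supportive answer to whether the effect holds after adjustment for the stratification factors and site. If curcumin works, the adjusted odds ratio will tend to look larger than it is. The P value next to it will also vary with the test that is reported.

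**Working it through.** **The plan's own figure.** The A'Hern design of 21 patients with at least 8 responders is reproduced exactly at a null rate of 20% and a target of 50%: P(X ≥ 8 | 21, 0.20) = 0.043 and P(X ≥ 8 | 21, 0.50) = 0.905. Dropout: 21 / 0.9 = 23.3, so 24, against the 25 per arm stated. That design sizes a single-arm rule and says nothing about a six-term model.

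**Slopes.** Treatment 1 + diabetes 1 + obesity 1 + fibrosis stage 1 + CKD 1 + site 1 = 6.

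**Expected responders at 26 per arm.**

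- 15% v 38%: 26 × 0.15 + 26 × 0.38 = 3.9 + 9.9 = 13.8
- 15% v 45%: 3.9 + 11.7 = 15.6
- 15% v 50%: 3.9 + 13.0 = 16.9
- With 10% missing counted as non-response, the first and last become 13.8 × 0.9 = 12.4 and 16.9 × 0.9 = 15.2

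For 14-16 responders, 14 / 6 = 2.3 and 16 / 6 = 2.7 per slope.

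**Bias when a real effect exists.** The six-term model was simulated with stratified blocks of 4, 2,500 trials per scenario. Assumed, because the protocol gives no figures: prevalences 0.5, 0.6, 0.35 and 0.3 for the four stratifiers, 0.5 for site, and none or moderate covariate effects. The adjusted fits are compared with the covariate-conditional odds ratio that generated the data, so non-collapsibility does not explain the excess. The unadjusted fit is compared with the marginal odds ratio. Entries are estimate ÷ truth, as geometric mean / median.

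| N, rates, missing | Responders | True adjusted OR | Maximum likelihood | Firth | Unadjusted |
|---|---|---|---|---|---|
| 52, 15% v 38%, 0 | 13.8 | 3.63 | 1.32 / 1.24 | 1.02 / 0.95 | 1.07 / 1.04 |
| 52, 15% v 50%, 10% | 15.2 | 5.57 | 1.41 / 1.34 | 1.01 / 0.94 | 1.08 / 1.06 |
| 50, 15% v 50%, 10% | 14.6 | 5.24 | 1.42 / 1.35 | 1.02 / 0.96 | 1.09 / 1.08 |
| 52, 15% v 50%, 0 | 17.0 | 6.06 | 1.48 / 1.38 | 1.02 / 0.97 | 1.09 / 1.06 |

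Across all scenarios run at N = 50-52, including fixed equal arms and strong covariate effects, the overstatement was 24-53% by median and 32-65% by geometric mean. With no or moderate covariate effects it was 24-44% and 32-52%. A separate simulation with prevalences of 50, 60, 30, 30 and 35% agrees. At 15% v 38% the true odds ratio is (0.38/0.62) / (0.15/0.85) = 3.5, and the median was 4.4 by maximum likelihood and 3.4 by Firth. At 15% v 45% the truth is (0.45/0.55) / (0.15/0.85) = 4.6, and the medians were 6.1 and 4.5. The unadjusted excess is only 4-9%, so most of the bias comes from the covariate load.

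**At the null (stratified blocks, N = 52).** The median odds ratio is 1.01-1.04, so there is no material bias. Rejection rates at nominal 5%:

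| Rate in both arms | Responders | Likelihood ratio | Wald | Firth, penalised likelihood ratio |
|---|---|---|---|---|
| 30% | 15.6 | 6.6% | 5.0% | 4.5% |
| 27% | 14.0 | 6.6% | 4.7% | 4.0% |
| 15% | 7.9 | 8.6% | 3.6% | 4.2% |

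Over all runs at N = 50-52, the likelihood-ratio size was 6.6-8.2% at 14-16 responders and 7.9-9.0% at the 15% null. Wald was between about 2.5% and 6%. At nulls of 15-20%, some coefficient was infinite in 11-36% of trials.

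**Power.** In the four effect scenarios above, in order: likelihood ratio 53.2, 76.6, 73.4 and 82.4%; Firth 44.9, 70.4, 67.3 and 77.8%; Wald 45.7, 70.1, 66.7 and 78.2%.

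**The case against.** The protocol does not say maximum likelihood, likelihood-ratio test or odds ratio, and estimation details are often left to a statistical analysis plan. The only adjusted measure it names is the Mantel-Haenszel relative risk. The model is supportive. The 38% is a go threshold and 45% appears nowhere in the protocol, and every covariate prevalence is assumed. Sampling noise at this size is also large: the median standard error of the log odds ratio is about 0.77, against a bias of about 0.27. Using fewer covariates would also reduce the problem.

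Most of this stands and limits the point. A reader might infer that the adjusted analysis gives about 8% false positives at 14-16 responders. The documents do not support that. The figure needs a likelihood-ratio test that the protocol never names, and it belongs mainly to nulls of 15-20% with about 8-10 responders. With stratified blocks and 14-16 responders the likelihood-ratio size is 6.6%, and the Wald test stays near or below 5%.

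What does not fall away is the bias. Maximum likelihood is the ordinary reading of an unqualified logistic regression, the protocol itself fixes the six terms and 52 patients, and the overstatement appeared under every set of assumptions tried. The Mantel-Haenszel relative risk is a separate calculation and does not correct the logistic fit.

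**Conclusion.** The point holds for the supportive model only. If curcumin has a real effect and the model is fitted by ordinary maximum likelihood, the adjusted odds ratio will be overstated by roughly 25-50%, and some coefficient may be infinite, mainly when responders are few. Without an effect there is no bias in the odds ratio, and whether the test is too liberal or somewhat conservative depends on the unnamed test.

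A reader might also infer that the trial's main conclusion is at risk. It is not: the Cochran-Mantel-Haenszel primary analysis and the 8-of-21 rule do not use this model.

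The size rests on 15% in the control arm, a working range of 38-50% on curcumin, and assumed covariate prevalences and effects. This is a cheap improvement, not a fault that threatens the design.

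**What to change.** In section 9.2, keep the same covariates and state that this supportive logistic model will be fitted by Firth's penalised likelihood, with the confidence interval and P value from the penalised profile likelihood. Report its odds ratio alongside the Mantel-Haenszel adjusted relative risk, not in place of it, so that the effect measure the protocol already names is kept.

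The cost is one sentence and a different fitting routine; the sponsor should confirm that the software named in section 9.5 can run it. Apparent power is about 5-8 points below that of the likelihood-ratio test, whose size is too large, and about the same as Wald.
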